- c. problem-solving Variable: IGDI problem-solving score
- d. global development Variable: Bayley III score

Hypothesis 2: Compared to the BAU group, the START-Play group will show greater sustained improvements from pre-intervention to one year since start of intervention (long-term effect) in:

- a. sitting Variable: Gross Motor Function Measure (GMFM) sitting scores
- b. reaching Variable: Number of toy contacts
- c. problem-solving Variable: IGDI problem-solving score
- d. global development Variable: Bayley III score

Hypothesis 3 (Mediation): Improvements in global development will be (at least) partially mediated by improvements in problem-solving as a function of the intervention at the end of the project (long-term proximal effect).

Variables: GMFM scores, toy contacts, IGDI problem-solving and Bayley III scores.

SECONDARY HYPOTHESES

Analysis of moderators

1. *Hypothesis:* Severity of motor impairment will have a significant influence on overall change in IGDI problem-solving, and motor scores, as well as Bayley III scores. Variable: Severity score (see Table 1)

2. *Hypothesis:* Factors external to the child (socialization opportunities [Modified Parent Child Interaction-Dyadic Mini Code scores (Censullo, 1991) (PCI-DMC)], and home environment (HOME Inventory [Bradley, 1993] & SES), will have a moderate effect on change in GMFM, problem-solving, and Bayley III scores.

Further analysis of motor variables

3. *Hypothesis:* The START-Play group will show posture control measures that are closer to normative values than the BAU group from pre to post intervention. This hypothesis tests additional variables quantifying sitting to supplement Primary Hypothesis 1. Variables: Kinematic measures taken from video analysis.

4. *Hypothesis:* Compared to the BAU group, the START-Play Intervention group will show greater improvements in duration of toy contact and object manipulation from pre to post intervention. This hypothesis tests additional variables quantifying reaching to supplement the

Primary Hypothesis 2. Variables: Unilateral and bilateral contact number and duration, and type of contact (i.e. hand open or closed; palmar or dorsal hand surface, manipulation variables).

iii. Research Design

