Evaluation of Secondary Hypotheses 1 & 2: Improvements in sitting, reaching, problem-solving and global development will be moderated by (1) internal variables: the severity of neuromotor disorder, health status, entry age, cognitive status at entry; and (2) external variables:

Figure 2. Mediated Effects Model for Hyp. 3 & 4

Note: RX = intervention phase; LT = follow-up phase; START-Play = assignment to condition; A,C = direct effects of the intervention on proximal & distal outcomes, B₁ & B₂ = effect of mediator(s) on other outcomes

socioeconomic status, compliance/attendance to home visits, the home environment (HOME), and overall amount of service to the family and child. Evaluation of these variables as moderators of the effect of the intervention on change in primary outcomes (sitting, reaching, problem solving and global development) will be done by modifying the LMM model equation used in evaluation primary hypothesis 2. Two three-way interaction terms, $TRT_{0i}RX_{it}MOD_{1i}$ and $TRT_{0i}LT_{it}MOD_{1i}$, where MOD_{1i} represents an individual moderator, will be added to the model to capture the intervention by time by moderator interaction. The simple effect of the moderator, MOD_{1i} , will be included as well as relevant 2-way interactions. All continuous variables will be mean-centered prior to forming cross-product interaction terms, and all categorical variables will be dummy coded prior to forming interaction terms. Each potential moderator will first be entered individually, and later in combination, with each primary outcome tested separately.

Evaluation of Secondary Hypothesis 3: Relative to infants in the BAU group, infants in the intervention group will show greater improvements in sitting control both post-intervention and at long-term follow-up. Evaluation of this secondary hypothesis will utilize the same LMM framework presented for evaluating primary hypotheses 1 and 2, with the exception that the outcome measures will be trunk forward bending, angular displacement, and velocity of trunk.

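### Secondary Hypothesis 1 is about severity and overall change, but the SAP names only tests of effect modification, at least 64 of them, with no stated error control

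*SAP*

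**What the plan says.** SAP section ii, like section 1 of the protocol, states Secondary Hypothesis 1 as: "Severity of motor impairment will have a significant influence on overall change in IGDI problem-solving, and motor scores, as well as Bayley III scores". Secondary Hypothesis 2 says that factors external to the child "will have a moderate effect on change in GMFM, problem-solving, and Bayley III scores". It names three such factors: "socialization opportunities [Modified Parent Child Interaction-Dyadic Mini Code scores (Censullo, 1991) (PCI-DMC"), the HOME Inventory and SES. Both hypotheses stand under a subheading on moderators.

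SAP section ix, on evaluating these two hypotheses, recasts them as moderation of improvement. The internal variables are "the severity of neuromotor disorder, health status, entry age, cognitive status at entry". The external ones are "socioeconomic status, compliance/attendance to home visits, the home environment (HOME), and overall amount of service to the family and child". The task is then given as "Evaluation of these variables as moderators of the effect of the intervention on change in primary outcomes", carried out by adding two three-way terms, TRT × RX × MOD and TRT × LT × MOD. The moderator's simple effect and the accompanying two-way terms are also fitted. On procedure: "Each potential moderator will first be entered individually, and later in combination, with each primary outcome tested separately".

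Three other places matter:

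- The model in section ix codes treatment 0 for usual services and 1 for START-Play.
- The error-control paragraph in section ix defines its family as the four primary outcomes.
- Section viii adds fidelity to the list of possible moderators.

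**The concern.** The hypothesis and its named test have different targets. An influence of severity on overall change means that more and less severely affected infants develop at different rates, whatever arm they are in. A treatment-by-time-by-severity term asks whether the benefit of START-Play depends on severity. Either can be true without the other. If severely affected infants progress more slowly but respond equally well to treatment, Hypothesis 1 is true, yet the named terms would give no sign of it. Severity also enters the primary model as a covariate, but only as a main effect on level, so that term does not address change either.

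The same section also generates many tests. The SAP argues that several outcomes call for error control, then fixes the family at the four primary outcomes. Nothing is said about the moderator tests, which reuse those outcomes for every moderator and both study phases.

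**Working it through.** The documents give no number of moderator tests, no alpha for them and no expected count of false positives, so there is no stated figure to reproduce.

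**Which coefficient answers Hypothesis 1**

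For one phase, let b be the coefficient of MOD × RX and c that of TRT × RX × MOD. With treatment coded 0/1:

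- severity effect on change under usual services: b
- severity effect on change under START-Play: b + c
- average over two equal arms: b + 0.5c
- named test: c = 0

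Hypothesis 1 concerns b + 0.5c. If severity acts equally in both arms, c = 0 and the named test rejects at about alpha, however large b is. The raw two-way coefficient b is not the overall effect either, because it describes only the usual-services arm. The same holds for LT.

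A simplified regression simulation illustrates this. The assumed inputs are 140 infants, 70 per arm, one continuous moderator, an overall effect of 0.4 SD and no effect modification, with 4,000 runs.

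| Term tested | Rejection rate |
|---|---|
| treatment × moderator (the kind of term named) | 4.4% |
| moderator, 0/1 treatment coding (usual-services arm) | 90% |
| moderator, centred treatment (overall effect) | 99.5% |

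The 140 comes from SAP section iv. The 0.4 SD is an assumption and affects only the last two rows.

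**How many tests**

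- Moderators in section ix: 4 internal + 4 external = 8
- Three-way terms per model: 2
- Outcomes, each tested separately: 4
- Total: 8 × 2 × 4 = 64

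With alpha .05 (stated only for the primary power analysis and assumed here) and every null true:

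- expected false positives: 64 × .05 = 3.2, whatever the correlation between tests
- chance of at least one, if independent: 1 − .95^64 = .96
- chance of at least one, simulated as 16 blocks of four correlated statistics: 95% at r = 0.3, 93% at 0.5, 89% at 0.7

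**How the count moves**

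| Scope | Tests | Expected at .05 |
|---|---|---|
| Section ix list, entered individually | 64 | 3.2 |
| Adding fidelity (section viii) | 72 | 3.6 |
| Adding fidelity and PCI-DMC | 80 | 4.0 |
| Section ix list, severity as two dummy variables | 72 | 3.6 |
| Section ix list, plus one full repeat in combination | 128 | 6.4 |
| Hypotheses as worded: severity 4 × 2, plus 3 factors × 3 outcomes × 2 | 26 | 1.3 |

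If the planned step-down method were applied across the four outcomes for each moderator and term, there would be 8 × 2 = 16 families. At most 16 × .05 = 0.8 of them would be expected to contain a false positive.

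**The lists side by side**

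PCI-DMC is named in Hypothesis 2 but appears in neither section viii's list of moderators nor section ix's. Fidelity is in section viii's list only. Reaching is tested for the external moderators in section ix, although Hypothesis 2 does not mention it.

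**The case against.** The strongest reply is that the documents, read together, point to effect modification. Both hypotheses sit under a moderator subheading, section viii calls the factors moderators, and section ix says improvements will be moderated by them. On that reading the three-way terms are right and one phrase in Hypothesis 1 is loose. This carries weight for Hypothesis 2, which does not say *overall*. A reader might infer that both hypotheses contradict their test, but the wording supports that only for Hypothesis 1. There the phrase is explicit and appears in both documents, so the conflict needs a decision.

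A second reply is that the two-way terms are in the model, so overall change can be estimated. That is correct, and a reader should not infer that the planned model cannot answer Hypothesis 1. But the SAP does not say that these terms decide anything, and under 0/1 coding the raw coefficients are not the overall effect.

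Third, these are secondary analyses, run after the primary questions, and silence on adjustment does not rule it out. That stands. A reader might also infer that about three spurious moderators will be reported. The documents do not support a flat prediction, because 3.2 requires every null to be true and an alpha that is not stated for these tests.

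Finally, one might double the detectable effects in section iv to gauge power for interactions. That rule needs an evenly split two-level moderator, while severity has three levels and section ix also provides for continuous moderators. The reaching figures in section iv also do not fit together under a fixed standard error. Power of 93% at d = 1.32 implies 80% power near 1.32 × 2.802/3.436 = 1.08, not 0.66. No power figure for moderators is claimed here.

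**Conclusion.** The point holds in three parts.

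1. For Hypothesis 1, the stated target and the named test differ. Followed as written, a true overall severity effect without effect modification would be detected only at about the alpha rate. This follows from the model and does not depend on the simulation's assumptions.
2. For Hypothesis 2, the target is ambiguous, and one of its named factors is absent from the analysis list.
3. At least 64 three-way tests are implied with no stated error rule. The 3.2 expected false positives, and the chance of at least one (96% if independent, about 89-95% for correlations of 0.7 to 0.3), hold only if all nulls are true and alpha is .05. That no adjustment is intended is inferred from silence.

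The primary hypotheses and their error control are not affected. This should be corrected, but it concerns secondary claims only.

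**What to change.** - Decide Hypothesis 1 on the severity-by-RX and severity-by-LT effects averaged over arms, by centring treatment or writing the averaged contrast explicitly. Do not use the raw two-way coefficients under 0/1 coding.
- State whether Hypothesis 2 concerns change averaged over arms or modification of the treatment effect, name the matching term, and say whether reaching is included.
- Keep the three-way terms for effect modification. Adjust the severity terms across the four outcomes with the step-down permutation method already planned.
- Label the other moderators exploratory. Report them as estimates with intervals, with Benjamini-Hochberg control, and cover the combined-entry round by the same rule.
- Use one moderator list in SAP sections ii, viii and ix, settling the place of PCI-DMC and fidelity.

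The cost is SAP wording and one contrast per phase from a model already planned. No new data are needed. The downside is that fewer moderator findings can be called confirmatory.

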- Bayley Scales of Infant and Toddler Development—Third Edition (Bayley III, Bayley, 2006), The Bayley III is a well known norm-referenced test designed to assess five key developmental domains: cognition, language, social-emotional, motor and adaptive behavior. Videotapes of this test will be scored to reach reliability of 90% agreement at the UW site.

4) Secondary Measures: These variables quantify factors related to the primary measures above. Secondary Measures for Sitting related to impairments in postural control:

Trunk alignment as an infant develops sitting posture has long been used as a clinical measure of postural control (McGraw, 1943; Bly, 1983; [name] et al, 1993). Movement and posture in sitting will be sampled monthly and quantified with kinematic measures from video.

Instrumentation: Quantification of sitting posture data will occur via a video taken from the side view of the infant ([name] et al, 1993). Data will provide:

- angle of forward bending during independent sitting,
- angular velocity from vertical to self-supported resting position, and
- angular displacement from vertical supported position to self-supported sitting position.

These variables are indicators of the control the infant is developing for maintaining upright sitting. Standardized positioning of child and camera will allow accurate use of the SIMI Move application to quantify the trunk control in sitting (90% agreement)(Surkar et al, 2013).

Data Collection and Analysis: The infant will be placed in a sitting position on the floor, and supported by the examiner; the examiner then removes their hands, which have been supporting the trunk. Measurement is taken from the point of the initial supported position to the end position independently assumed by the infant, and is quantified by degrees. Data are collected for 3 trials while the child attempts to maintain sitting. *See Figure 8 Appendix B.*

Secondary Measures for Reaching (documents impairments in reaching and object exploration):

These variables are coded from video to further quantified reaching:

- Age of reach onset and number infants that are reaching at each age. An infant is ‘reaching’ the first session he contacts the toy more than 5 times in 3 min of trial time ([name] et al 2004).
- Percent of time each hand is in contact with the toy (aka Contact Duration).
- Number of toy contacts with both hands

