- Hand position at initial contact and during contact: open/closed hand, ventral/dorsal surface.

Secondary Measures: Child and Family Characteristics

Child characteristics (Severity, Cognitive, Age, Health) will be recorded, respectively, from previously described Severity Index, Bayley III scores, and a Demographic questionnaire and Health questionnaire, which are both completed by parents. Environmental factors include: 1) Parent/child interaction (PCI-DMC) See Figure 9, Appendix B., 2) Home environment (HOME scale [Elardo & Bradley, 1981]), 3) SES, 4) program attendance/participation (visit counts), and 4) overall amount of services (Therapy Services questionnaire). The Home Observation for Measurement of the Environment (HOME) Inventory – Infant/Toddler version assesses the home

environment including adult/child contact, social/cultural experiences, physical environment, and access to toys. SES will be measured on a Demographic questionnaire completed by parents. Program attendance will be recorded by the number of accomplished visits, documented by the therapist visiting the home. Amount of therapy will be recorded via the Therapy Service questionnaire completed by parents (see Appendix B).

vi. Fidelity of implementing the START-Play intervention

Our fidelity approach will determine the degree to which all elements of the START-Play intervention are delivered across treatment and control conditions (Knoche et al, 2010). We will assess dosage, adherence, quality, participant responsiveness, and program differentiation (Berkel et al., 2011; Cordray & Pion, 2006; Dane & Schneider, 1998; O'Donnell, 2008) with three primary measures: (1) START-Play Home Visit Coding Guide (adapted from the Home Visit Observation Form; McBride & Peterson, 1997) (see Appendix B); (2) Therapy Services Form (adapted from Westcott & Effgen, 2011; Appendix B); and (3) Home Activity Log (Appendix B). Both the experimental and BAU groups will be measured using these instruments. Relevant fidelity metrics for dosage, adherence and quality (or some combination) will be derived in consultation with our team from the Statistics and Research Methodology Unit of CYFS, allowing us to account for fidelity as a covariate in the analysis of treatment effects.

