Evaluation of Secondary Hypothesis 4: Infants in the intervention group will show greater improvements in reaching from pre- to post-intervention than the infants in the BAU group. Evaluation of this secondary hypothesis will also utilize the same LMM framework presented for evaluating primary hypotheses 1 and 2, with the exceptions that (a) the outcome measures will be unilateral and bilateral contact number and duration, and type of contact (i.e. hand open or closed; palmar or dorsal hand surface), and (b) that only data through the end of intervention will be used (i.e. there will be no LT_{it} term in the model). As these outcomes are categorical, we will utilize the capacity for SAS PROC GLIMMIX to implement a *generalized* LMM framework by including a logit link function and a cumulative or generalized logit link function to model dichotomous outcomes and polytomous outcomes (more than 2 categories), respectively.

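### The SAP calls every Secondary Hypothesis 4 reaching outcome categorical and names only logit-type links, although contact number is a count and contact duration a percent of time

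*SAP*

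**What the plan says.** SAP section ix, Evaluation of Secondary Hypothesis 4, sets out the analysis in three steps.

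- Outcomes: "the outcome measures will be unilateral and bilateral contact number and duration, and type of contact". Hand open or closed, and palmar or dorsal surface, are given as the types.
- Base model: the evaluation "will also utilize the same LMM framework presented for evaluating primary hypotheses 1 and 2". Two exceptions are listed: the outcomes differ, and data stop at the end of treatment, so the follow-up (LT) term is dropped.
- Distribution and link: "As these outcomes are categorical, we will utilize the capacity for SAS PROC GLIMMIX to implement a" generalized version of the mixed model, "by including a logit link function and a cumulative or generalized logit link function to model dichotomous outcomes and polytomous outcomes".

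SAP section v, Secondary Measures for Reaching, defines the variables:

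- duration: "Percent of time each hand is in contact with the toy (aka Contact Duration";
- two-handed contact: "Number of toy contacts with both hands";
- type of contact: "Hand position at initial contact and during contact: open/closed hand, ventral/dorsal surface".

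On data collection for the primary toy-contact measure, SAP section v describes six trials of 30 seconds and three levels of support, and gives 15 trials in total. Protocol section 4 describes the same procedure and gives 18.

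**The concern.** The sentence on distribution refers back to the whole outcome list, but what it says is true of only one kind of outcome on that list. A count and a percentage of time are neither dichotomous nor polytomous. Following the sentence literally would mean cutting them into classes, and no document says where.

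What is at stake is pre-specification. Duration is the first variable that SAP section ii names in this hypothesis, which predicts "greater improvements in duration of toy contact and object manipulation from pre to post intervention". If the paragraph can be read as two different models, the choice for duration and number stays open until the data are available.

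The trial total is a separate matter of consistency. It describes how a primary measure is collected, and the documents give two values.

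**Working it through.** **Model for each outcome.** No sample-size or power formula applies here, so the check sets the definitions beside the named links.

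| Outcome | How the SAP describes it | Dichotomous or polytomous? | Cut-points given? |
|---|---|---|---|
| Contact number | a number of contacts | no, a count | none |
| Contact duration | percent of time | no, bounded 0–100% | none |
| Type of contact | open/closed; palmar (ventral)/dorsal | yes | not needed |

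The paragraph can then be followed in two ways for number and duration.

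1. *Take the distribution sentence at its word.* Number and duration become classes modelled with logit-type links. The treatment effect is a difference between arms in the change over time of the log odds of being in, or above, some class. That quantity depends on cut-points that do not exist in either document.
2. *Take the reference to the primary model at its word.* Number and duration stay as measured. With the LT term removed, the effect is γ11, the between-arm difference in slope during treatment, in contacts per month or percentage points per month (the SAP measures time in months).

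These are different estimands on different scales, and the two listed exceptions do not separate outcomes by type. The general commitment in section ix to inspect distributions and modelling assumptions does not assign a model to either outcome.

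A logit link can be used for a proportion, for example with a beta distribution. The SAP does not provide for that: it ties its links to dichotomous and polytomous outcomes and names no distribution for a proportion or a count.

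**Trial total.** Inputs: six trials, 30 seconds each, three support levels (SAP section v); totals of 15 (SAP) and 18 (protocol).

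- The SAP's figure is not reproduced: 6 × 3 = 18, not 15. Reading six as the overall total gives 6, also not 15.
- 15 would need 15 / 3 = 5 trials per level, which neither document states.
- The protocol's 18 is reproduced exactly.
- Difference: 18 − 15 = 3 trials. Observation time is 18 × 0.5 = 9.0 min against 15 × 0.5 = 7.5 min, a difference of 1.5 min.
- The reach-onset definition in SAP section v uses 3 min of trial time. Six trials make 6 × 0.5 = 3.0 min; five make 2.5 min. This agrees with six per level but does not prove it.

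**The case against.** The best defence is that the distribution sentence is only loosely worded. The outcome list ends with type of contact and its examples, and the links named are the right ones for such variables. On that reading the logit-type links serve type of contact only, and number and duration stay in the linear mixed model already invoked. Nothing in either document suggests that anyone meant to categorise a count or a percentage. This is plausible, and the fix below adopts it. It does not remove the point, because the sentence covers the listed outcomes without exception and a reader has to override it to reach the sensible model.

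It is also fair to say that a different model for secondary outcomes would not by itself contradict the primary analysis. They are different variables, and they lie outside the four-outcome family for which the SAP controls the error rate.

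A reader might want to count how many outcomes are affected. The documents do not support a firm tally. Hand position is coded both at initial contact and during contact, and the unit of analysis (contact, trial or visit) is not stated, so the number of type-of-contact variables is open. A reader might also infer a loss of power from categorisation, but with no cut-points stated there is nothing to calculate.

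On the trial total, the defence is that 15 is the lone outlier and looks like a slip. That may well be so; it still needs correcting.

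**Conclusion.** The analysis paragraph for Secondary Hypothesis 4 is wrong as written for contact number and contact duration, and it leaves two models open for them. This rests only on the SAP's own definitions and on the plain scope of the distribution sentence. It is worth fixing but limited in reach: it concerns secondary outcomes, and the primary toy-contact analysis, the stated power and the error-rate control are unaffected. No effect on results is estimated.

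The trial total is a separate, minor inconsistency of 15 against 18. A reader might infer that a 15-trial session would give a total count one-sixth lower (1 − 15/18 = 0.167). That would need contacts to be summed over all trials at a constant rate, and neither document says how trials are combined. Nor do the documents show that sites ran different totals or that the arms were treated differently. The reaching power figure is not derived from the trial count. No claim is made about counts, power or bias.

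**What to change.** In SAP section ix, Evaluation of Secondary Hypothesis 4:

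- Limit the word *categorical*, and the logit, cumulative-logit and generalized-logit links, to type of contact.
- State that contact number and percent contact duration are analysed without categorisation, in the same linear mixed model as the primary toy-contact outcome, from baseline to the end of treatment and without the LT term.
- If a sensitivity analysis is wanted (negative binomial for number, beta for percent duration), run it unconditionally and state how exact 0% and 100% are handled. Otherwise omit it. Making it depend on an undefined failure of the assumption checks would bring back the discretion that the change is meant to remove.

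Separately, reconcile the toy-contact entries in SAP section v and protocol section 4 to one number of trials, stated identically in both.

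The cost is wording only. GLIMMIX is already the named software, and no further data are needed.
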